Investigator Signature	Date

Printed Name	

Institution Name	

Address	
_____	_____
City, State, Postal Code, Country	Phone Number

List of Abbreviations

█	█
AE	Adverse event
CI	Confidence interval
DAXI	DaxibotulinumtoxinA
DRC	Data Review Committee
eCRF	Electronic case report form
FASE	Facial Age Self Evaluation
FWS	Facial Wrinkle Severity
GAIS	Global Aesthetic Improvement Scale
GCP	Good Clinical Practice
GL	Glabellar lines
ICF	Informed consent form
IEC	Independent Ethics Committee
IGA-LCWS	Investigator Global Assessment Lateral Canthal Wrinkle Severity
IM	Intramuscular
IRB	Institutional Review Board
kDa	Kilodalton
KM	Kaplan-Meier
LCL	Lateral canthal lines
MedDRA	Medical Dictionary for Drug Regulatory Affairs
█	█
NSAID	Nonsteroidal anti-inflammatory drug
PLCWS	Patient Lateral Canthal Wrinkle Severity
PHI	Protected health information
PI	Principal Investigator
SAE	Serious adverse event
SNAP-25	25 kDa synaptosome associated protein
SOA	Schedule of Assessments
TEAE	Treatment-emergent adverse event
UPT	Urine pregnancy test
WOCBP	Women of childbearing potential

	
[REDACTED]
 
■ [REDACTED] 
[REDACTED]
 
■ [REDACTED]■ [REDACTED]■ [REDACTED]
--	---

Study Population:

Approximately 64 male and female subjects, 18-65 years old, will be enrolled into the study. Subjects must meet all the inclusion criteria and none of the exclusion criteria to be eligible for this study.

Inclusion Criteria:

To be eligible for participation, subjects must:

1. Provide written informed consent consistent with International Conference on Harmonisation (ICH)-Good Clinical Practice (GCP) guidelines and local laws, including authorization to release health information, signed prior to any study procedures being performed
2. Be outpatient, male or female subjects, in good general health, 18-65 years old
3. Have a score of moderate (2) or severe (3) LCL at maximum smile effort as assessed by the IGA-LCWS (scores must be consistent bilaterally)
4. Have a score of moderate (2) or severe (3) LCL at maximum smile effort as assessed by the PLCWS (scores must be consistent bilaterally)
5. Have sufficient visual acuity without the use of eyeglasses (contact lens use is acceptable) to accurately assess their facial wrinkles
6. Be willing to refrain from receiving facial fillers, laser treatments, use of any product that affects skin remodeling, or a product that may cause an active dermal response in

the treatment areas (e.g., above the oral commissures) from screening through the end of the study

7. All women of childbearing potential (WOCBP) must have a negative urine pregnancy test (UPT) result at the Screening Visit and must practice an effective method of contraception throughout the study (e.g., oral contraceptive pill, injection, implant, patch, vaginal ring, intrauterine coil, intrauterine device, tubal ligation, barrier method) used WITH an additional form of contraception (e.g., sponge, spermicide or condom); abstinence; no heterosexual intercourse; or has a vasectomized partner (refer to Section 5.6 for additional information)
8. Able to understand the requirements of the study and be willing and able to follow all study procedures, attend all scheduled visits, and successfully complete the study.

Exclusion Criteria:

Subjects will not be eligible for study participation if they meet any of the following criteria:

1. Any neurological condition that may place the subject at increased risk with exposure to botulinum toxin type A, including peripheral motor neuropathic diseases, such as amyotrophic lateral sclerosis and motor neuropathy, and neuromuscular junctional disorders, such as Lambert-Eaton syndrome and myasthenia gravis
2. Any history of facial nerve palsy (e.g., Bell’s Palsy) or muscle weakness or paralysis in the treatment areas
3. Active skin disease, infections, or inflammation at the injection sites
4. History of or current significant facial asymmetry, eyelid ptosis or history of same, excessive dermatochalasis, deep dermal scarring, thick sebaceous skin, or inability of investigator to completely or almost eliminate the LCL by physically spreading lateral canthal area apart while at rest
5. History of or current significant brow ptosis, significant brow asymmetry at rest or on brow elevation.
6. A score of 2 or higher in any category of the Regional House-Brackmann Facial Nerve Grading System at screening
7. Previous treatment with botulinum toxin type A in the face within 6 months prior to screening
8. Has had within the last 6 months prior to screening, or plans to receive, any botulinum toxin treatment (other than study treatment)
9. Has had within the last 6 months, or plans to receive, treatment with >200 U of any botulinum toxin anywhere in the body outside of the face within the last 6 months prior to screening through the end of the study

[Redacted text block]

[REDACTED]

[REDACTED]

Overall Design:

This is a phase 2a, multicenter, open-label, dose-escalation study to evaluate the safety and efficacy of DAXI for injection for the treatment of subjects with moderate to severe LCL. This study will be conducted at 4 sites in the United States.

Approximately 64 subjects (18 to 65 years old) with moderate to severe LCL will be enrolled sequentially into 1 of 4 treatment cohorts (approximately 16 subjects per cohort) [REDACTED]

[REDACTED] Investigators will make all reasonable efforts to enroll equal proportions of subjects with moderate and severe LCL (based on baseline assessments) in each dosing cohort.

The total study duration will be up to 38 weeks, including up to 2 weeks for screening. Subjects will be followed for a minimum of 24 weeks from LCL treatment and up to 36 weeks or until scores on the maximal expression IGA-LCWS and PLCWS return to baseline, whichever occurs first. Subjects will then have a Final Evaluation Visit. Baseline, unless otherwise stated, refers to the last available assessment prior to LCL treatment (Day 1 Visit).

All treatments will be IM injections administered by the principal investigator (PI). [REDACTED]

[REDACTED]

[REDACTED]

[REDACTED]
 
[REDACTED]
 
[REDACTED]
 
[REDACTED]
 
[REDACTED] Revance has this right to stop or terminate the study at any time for any reason at their discretion or in consultation with the DRC.

Study Visits:
 
Study visits will occur at the Screening Visit (Day -14), Treatment Visit (Day 1), a safety follow-up phone call at Week 1, and follow-up visits at Weeks 2, 4, 8, 12, 16, 20, 24, 28, 32, and 36. Baseline for all efficacy assessments, unless otherwise noted, will be the last available assessment prior to LCL treatment (Day 1 Visit).


Efficacy Evaluations:
 
• IGA-LCWS• PLCWS• GAIS• FASE• FACE-Q™ Appraisal of Lines: Crow's Feet Lines 
Baseline for all efficacy assessments associated with LCL severity, unless otherwise noted, refers to the last available assessment prior to LCL treatment (Day 1 Visit). Efficacy outcomes derived from the above list of assessments will be summarized descriptively by dose group and by timepoint. Count and proportion will be provided for responder endpoints (defined as proportion of subjects achieving certain status). Kaplan-Meier (KM) curves will be plotted by treatment group for each time-to-event endpoint to assess median duration of effect at maximum smile and at rest for selected endpoints. Dose-response will be explored using logistic regressions on the response rates (of key responder endpoints) and using log-rank test on the time-to-event endpoints. The effect of study center and baseline severity on the treatment outcome will also be explored.

Safety Evaluations:

- Clinical laboratory tests (hematology, serum chemistry, prothrombin time [PT], urinalysis)
 - [REDACTED]
 - [REDACTED]
- Injection site evaluation
 - [REDACTED]
- Concomitant therapies/medications
- Collection of adverse events (AEs)
 - [REDACTED]
- Vital signs
- Physical examination: [REDACTED]

All TEAEs occurring during the study will be recorded and classified according to Medical Dictionary for Drug Regulatory Affairs (MedDRA) terminology. All reported TEAEs will be summarized, in terms of the number of subjects reporting events, system organ class, preferred term, severity, relationship to study drug, and severity. For summarization of event causality and severity, subjects will be counted only once within a system organ class or preferred term for a given event using the event with the greatest relationship for causality and the highest severity. A summary of AEs leading to discontinuation will also be provided.

A by-subject listing of any SAEs will be provided and all SAEs will be summarized by severity and relationship to study treatment.

All AEs, including TEAEs, and SAEs will be summarized for the study overall and by dose group.

Clinical laboratory tests, including serum chemistry, hematology, PT (at the Screening Visit only), and urinalysis will be collected at the Screening Visit, Week 4, and Week 36 or Final Evaluation Visit, if applicable. [REDACTED]

[REDACTED]. A UPT for all WOCBP will be performed at the Screening Visit, Day 1, and Week 36 or the Final Evaluation Visit, if applicable.

[REDACTED]

[figure not shown]
Other Evaluations:

[figure not shown]
- [REDACTED]
- [REDACTED]
- [REDACTED]
- [REDACTED]

[figure not shown]
Number of Subjects:

Approximately 64 subjects are expected to participate in this study. Refer to Section 9.2 for additional information on sample size determination.

Disclosure Statement: This is an open-label, dose-escalation study with 4 treatment arms; neither subjects nor investigators/study staff will be blinded. All subjects will receive DAXI for injection for the treatment of moderate to severe LCL.

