2. INTRODUCTION

The formation of wrinkles at the corners of the eyes, which are referred to as crow's feet lines or LCLs, are one of the primary signs of aging that can negatively impact the assessment of a person's age. These dynamic lines appear during facial muscle contractions, like smiling, and over time can become permanent or static, meaning that they are still visible when without muscle contraction (Kane, 2015).

Minimally-invasive injectable treatments have become the most common aesthetic procedure worldwide (Baumann, 2016) with an increase in frequency over the last decade since the first approval of botulinum neurotoxin Type A (OnabotulinumtoxinA; BOTOX[®] Cosmetic; [package insert]. Allergan, Inc., 2017). This is largely the result of an exceptional safety profile, as well as the ability of botulinum neurotoxin Type A to rejuvenate and enhance the facial area when compared with more invasive cosmetic procedures.

Botulinum neurotoxin is produced by *Clostridium botulinum*, which is a gram-positive, spore-forming, anaerobic bacterium (Carruthers, 2015a). There are 7 distinct types (A-G), only types A and B have established clinical uses due to a longer duration of action compared to the other types (De Boulle, 2007). Botulinum neurotoxin Type A blocks acetylcholine release into the neuromuscular junction, which prevents muscle contractions in the injected area. The onset of muscle weakening typically begins within 48 hours after treatment and usually lasts between 4 and 5 months, although some patients have reported shorter or longer durations (Nestor, 2017; Carruthers, 2015; De Boulle, 2007).

The presence of facial lines at rest result from a combination of factors, including repeated facial muscle contractions, structural skin remodeling that occurs with aging, and damage from excessive sun exposure (Carruthers, 2016). Carruthers, et.al., identified 4 distinct patterns for lateral canthal lines: full-fan, lower-fan, central-fan, and upper-fan. The description of these lines emphasizes the orientation of the lines in the lateral canthal area and nearby facial regions. As the dynamic patterns for LCL are further elucidated, it has become possible for experienced practitioners to customize treatment of the lateral canthal region to match the pattern of a patient's lateral canthal lines.

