4.4. Visit Schedule

A Screening Visit will be conducted up to 2 weeks prior to enrollment, and subjects will receive investigational product at baseline (Day 1). Following treatment, subjects will complete a paper diary for 2 weeks to capture their assessment of improvement in the appearance of LCL. A follow-up safety phone call will be conducted at Week 1. Post-treatment on-site follow-up visits

will occur at Weeks 2, 4, 8, 12, 16, 20, 24, 28, 32, and 36. The total study duration will be up to 38 weeks, including up to a 2-week screening period. Subjects will be followed for a minimum of 24 weeks post-treatment and up to 36 weeks or until scores return to baseline for the maximal expression IGA-LCWS and PLCWS or until the Week 36 Visit, whichever occurs first. Subjects will then have a Final Evaluation Visit.

Subjects will be evaluated for LCL severity using the Revance-validated 4-point IGA-LCWS and PLCWS at rest and at maximum smile effort.

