5.1. Inclusion Criteria

To be eligible for participation, subjects must:

1. Provide written informed consent consistent with International Conference on Harmonisation (ICH)-Good Clinical Practice (GCP) guidelines and local laws, including authorization to release health information, signed prior to any study procedures being performed
2. Be outpatient, male or female subjects, in good general health, 18-65 years old
3. Have a score of moderate (2) or severe (3) LCL at maximum smile effort as assessed by the IGA-LCWS (scores must be consistent bilaterally)
4. Have a score of moderate (2) or severe (3) LCL at maximum smile effort as assessed by the PLCWS (scores must be consistent bilaterally)
5. Have sufficient visual acuity without the use of eyeglasses (contact lens use is acceptable) to accurately assess their facial wrinkles
6. Be willing to refrain from receiving facial fillers, laser treatments, use of any product that affects skin remodeling, or a product that may cause an active dermal response in the treatment areas (e.g., above the oral commissures) from screening through the end of the study
7. All women of childbearing potential (WOCBP) must have a negative urine pregnancy test (UPT) result at the Screening and Baseline Visits and must practice an effective method of contraception throughout the study (e.g., oral contraceptive pill, injection, implant, patch, vaginal ring, intrauterine coil, intrauterine device, tubal ligation, barrier method) used WITH an additional form of contraception (e.g., sponge, spermicide or condom); abstinence; no heterosexual intercourse; or has a vasectomized partner (refer to Section 5.6 for additional information)
8. Able to understand the requirements of the study and be willing and able to follow all study procedures, attend all scheduled visits, and successfully complete the study.

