9.4.1. Efficacy Analyses

Unless otherwise noted, baseline for all efficacy assessments refers to the last available assessment prior to LCL treatment. Efficacy outcomes will be summarized. Descriptive statistics will be provided for all efficacy variables at all timepoints.

The primary efficacy endpoint will be the proportion of subjects achieving a score of 0 or 1 (none or mild) in LCL severity assessed by IGA-LCWS at maximum smile. The LCLs will be evaluated on both sides of the face and both scores will be recorded. If different ratings are obtained from the left and the right sides of the face, subjects will be scored using the higher (i.e., more severe) rating. The dose response in the proportion of responders at Week 4 will be explored using the logistic regression stratified by baseline LCWS severity and study center. Additional measures to assess the effectiveness outcomes will include the investigator GAIS evaluated at maximum smile at each visit. Various responder endpoints associated with the LCWS, such as achieving certain status or certain magnitude of improvement from baseline, will be derived from these effectiveness outcomes for each visit. These responder endpoints will be analyzed by statistical models similar to that for the primary endpoint.

Duration of response will be evaluated by various time-to-event endpoints. Kaplan-Meier (KM) curves will be plotted by dose group for each time-to-event endpoint.

Responder and time-event endpoints defined based on subject assessments for LCL wrinkle severity (such as PLCWS and the subject GAIS for LCL) will be summarized in the same way as those by investigator assessments. Similarly, the endpoints defined based on scores assessed at rest will be summarized in the same way as those on scores assessed at maximum smile.

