2.1.1 Primary Objective

The primary study objective is to evaluate the efficacy and safety of DAXI for injection in the treatment of dynamic lateral canthal lines (LCL).

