6.5.1 Primary Efficacy Analysis

The proportion of subjects achieving a score of 0 or 1 (none or mild) in LCL severity at maximum smile on the IGA-LCWS at Week 4 after LCL treatment will be summarized. An exact 95% confidence interval for the individual proportions will be provided. A Cochran-Mantel-Haenszel test of association, stratified by baseline IGA-LCWS severity and study center, will be performed. In addition, an exact Cochran-Armitage test for trend, ignoring the stratification factors, will be performed. If the Cochran-Mantel-Haenszel test is significant at the 0.05 significance level, then a linear regression on response will be performed with categorical dose and site as predictors. An unstratified logistic regression analysis may still be used to explore the dose-response relationship.

Additionally, the change from baseline in LCL Severity at Week 4 on the IGA-LCWS at maximum smile will be analyzed using a general linear model with change from baseline as the dependent variable. The model will include baseline severity and study center as fixed categorical effects. The least-square means and standard errors will be presented. Additionally, the differences between dose groups will be presented with corresponding 95% confidence intervals.

[REDACTED]

[REDACTED]

[REDACTED]

[REDACTED]

Statistical Analysis Plan for 1820205

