6.5.4 Adjustments for Covariates

The analysis of the primary endpoint requires a regression model to be run, where the baseline IGA-LCWS severity and study site are included in the model as covariates.

[REDACTED]

[REDACTED]

[REDACTED]

[REDACTED]

[REDACTED]

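### The baseline at-rest grade is collected but enters no visible Week 4 maximum-smile model; adding it as one main effect is an optional, low-cost improvement

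*Protocol*

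**What the plan says.** **Collection.** Protocol 4.4 has subjects evaluated on the "IGA-LCWS and PLCWS at rest and at maximum smile effort". Protocol 8.3.1 and 8.3.2 repeat this for each side of the face, and 8.3.2 names Screening and Day 1 for the subject scale. The investigator's visits are set by a schedule that is not in the public copy.

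**Eligibility and balance.** Inclusion criterion 3 fixes the smile grade only: "Have a score of moderate (2) or severe (3) LCL at maximum smile effort as assessed by the IGA-LCWS". Investigators are asked to balance moderate against severe within each cohort. No similar aim is stated for the at-rest grade.

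**Static lines.** The Protocol Introduction says that dynamic lines "over time can become permanent or static, meaning that they are still visible when without muscle contraction".

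**Week 4 analysis.**
- Protocol Synopsis, Efficacy Evaluations: "The effect of study center and baseline severity on the treatment outcome will also be explored".
- Protocol 9.4.1: dose response is "explored using the logistic regression stratified by baseline LCWS severity and study center".
- SAP 6.5.1, change from baseline: "The model will include baseline severity and study center as fixed categorical effects".
- SAP 6.5.1, response: a CMH test stratified by baseline IGA-LCWS severity and center; an exact Cochran-Armitage test that ignores the strata; if the CMH test is significant at 0.05, a linear regression on dose and site; and possibly an unstratified logistic regression.
- SAP 6.5.4: "the baseline IGA-LCWS severity and study site are included in the model as covariates".

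None of these names the at-rest grade.

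**The concern.** The SAP's primary objective concerns dynamic lines, and the endpoint is an absolute grade of 0 or 1 at maximum smile. Smiling adds lines to those already present at rest. If the smile grade cannot fall below the at-rest grade, a subject at grade 2 or 3 at rest can respond only if the static line itself improves, whatever the dose does to the muscle. Two subjects with the same baseline smile grade could then have different chances of response, and the planned covariates would not separate them.

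The design makes this matter more. Cohorts are small and not randomized, and Cohorts 3 and 4 enroll after Cohorts 1 and 2, so a difference in static lines could be systematic as well as accidental. Such a difference would be read as part of the dose effect. Static lines would also add unexplained variance to every dose contrast. A baseline measurement that could address both problems is already being collected.

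**Working it through.** **Inputs from the documents:** 4 cohorts of about 16 (4 × 16 = 64, as stated); 4 centers; two severity levels; no power basis for the sample size. There is no planned precision figure to reproduce.

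**Assumed inputs (not in the documents):** proportion q at grade 2 or 3 at rest, 20–50%; effect e of that state on response, 10–40 points; overall response 60%.

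**1. Chance imbalance between two cohorts.** SD = √(2q(1−q)/16).
- q = 0.20: √0.0200 = 14.1 points
- q = 0.35: √0.0284 = 16.9 points
- q = 0.50: √0.0313 = 17.7 points

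A gap of 25 points or more between the highest and lowest of four cohorts occurs in about 40% (q = 0.20) to 60% (q = 0.50) of trials.

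**2. Effect on a two-cohort response difference.** The shift has SD e × (SD above). The smallest value is 0.10 × 14.1 = 1.4 points and the largest 0.40 × 17.7 = 7.1 points. The total SE is √(2 × 0.6 × 0.4/16) = √0.03 = 17.3 points. The largest share of variance is 0.0707²/0.03 = 16.7%. With e = 20 points and q = 0.20 it is 0.0283²/0.03 = 2.7%.

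**3. Gain from one main effect.** This used 3,000 simulated trials per setting and a linear model on response with dose, severity and center. At-rest grade 2–3 was assumed in 20% of moderate and 50% of severe subjects. The table gives the SD of the top-minus-bottom dose contrast.

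| At-rest odds ratio | Without term | With term | Change in SD | Change in variance |
|---|---|---|---|---|
| 1 | 0.16866 | 0.16996 | +0.8% | +1.5% |
| 3 | 0.17524 | 0.17195 | −1.9% | −3.7% |
| 8 | 0.17523 | 0.15981 | −8.8% | −16.8% |

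**4. What blocking would imply.** Let m be the response rate when no static line blocks it (assumed 60–80%), and f the chance that the static line falls a grade (assumed 30–60%). Response among subjects at grade 2–3 at rest is then m × f.
- Weakest case: 0.60 versus 0.60 × 0.60 = 0.36, a gap of 24 points and an odds ratio of 1.50/0.5625 = 2.7.
- Strongest case: 0.80 versus 0.80 × 0.30 = 0.24, a gap of 56 points and an odds ratio of 4.0/0.316 = 12.7.

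Simulating this mechanism with 20–35% at grade 2–3 at rest cut the variance of the top-versus-bottom contrast by about 3–19% for change and 3–21% for response.

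**5. Imbalance that follows dose order.** Suppose there is no dose effect and the at-rest counts are 7, 6, 4 and 3 of 16. Cohorts 1 and 4 then differ by 4/16 = 25 points. The spurious responder difference is 0.25 × 24 = 6 to 0.25 × 56 = 14 points.

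**6. False positives.** With imbalance left to chance, a linear dose-trend test rejected in 4.2–5.3% of null trials without the term and 4.4–5.1% with it. Given the 7/6/4/3 pattern, the rates were 6.7–10.5% and 4.7–5.6%. A dose-ordered pattern at least that extreme arises by chance in about 3–6% of trials in that direction.

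**7. Why not a CMH stratum.** Severity by center gives 2 × 4 = 8 strata, or 64/8 = 8 subjects each and 2 per dose. Adding at-rest grade gives 16 strata, 4 subjects each and 1 per dose. Simulated power went from 0.54 to 0.46 (odds ratio 1), from 0.53 to 0.46 (odds ratio 3), and stayed at 0.41 (odds ratio 8).

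**The case against.** The strongest reply is that nothing here is an error. The plan prespecifies sensible covariates, Protocol 9.4 calls group comparisons exploratory, and other prognostic factors could be proposed in the same way. This stands, and it sets the priority.

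The blocking mechanism is also assumed. The Introduction says that static lines exist. It does not say that they prevent a 0 or 1 at maximum smile, or how common grade 2–3 at rest is. Exclusion criterion 4 in the Synopsis removes subjects whose lines cannot be nearly flattened by spreading the skin at rest. That partly limits the group in question, although it caps no at-rest grade. This stands too, and it is why the range starts at no gain.

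A reader might infer that omitting the covariate inflates the type I error of the dose comparisons. It does not under chance imbalance (step 6): nominal error rates and intervals already allow for that. Bias arises only if the imbalance is systematic or happens to follow dose order, and the documents give no evidence of drift. A reader might also expect more power for the planned responder tests. The CMH and Cochran-Armitage tests would be unchanged, and the trend test in step 6 is not one the SAP plans.

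Finally, parts of SAP 6.5 are blacked out, and further at-rest or covariate analyses may be there. SAP 6.2 does tabulate baseline IGA-LCWS and PLCWS by cohort, without naming the at-rest score.

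**Conclusion.** The point holds as an optional improvement to an exploratory analysis. The at-rest grade is collected, no visible Week 4 maximum-smile analysis uses it, and there is a plausible reason to expect it to be prognostic. If it is not, the term gains nothing and costs under 1% in the SD of a contrast. If static lines block response, the variance of a dose contrast falls by roughly 3–20%. The main value is protection against a systematic or dose-ordered difference between non-randomized cohorts, worth about 6–14 points of responder rate in the example in step 5. All these sizes rest on assumed prevalence and effect, not on figures in the documents. The documents do not support the stronger statement that static lines prevent response at any dose.

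**What to change.** In SAP 6.5.1 and 6.5.4, add baseline at-rest IGA-LCWS (0–1 versus 2–3) as a single main effect in the Week 4 general linear model and in the linear regression on response. At minimum, prespecify these as sensitivity models. Use the more severe side, as Protocol 9.4.1 does for the endpoint, and state that the existing baseline severity term is the maximum-smile grade, so that the two are not confused. Leave the CMH strata and the Cochran-Armitage test as they are. In SAP 6.2, tabulate the baseline at-rest grade by cohort.

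The cost is one or two SAP sentences, one table row and no new data. Residual degrees of freedom go from 64 − (1 + 3 + 1 + 3) = 56 to 55 in the general linear model, and from 64 − (1 + 3 + 3) = 57 to 56 in the regression on response.
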